8) Study endpoints

Among 10 stages 3-4 CKD patients with persistent, mild hyperkalemia, we will evaluate, in a quasi-experimental, controlled feeding study, the efficacy of patiomer for maintaining normal serum potassium concentrations when following a plant-rich diet that includes high-potassium fruits and vegetables, as well as the effects of this diet on health outcomes. The participants will be transitioned gradually to a plant-rich diet, as outlined further below.

The interventions will be evaluated primarily in terms of serum potassium concentrations, but health outcomes will also be assessed, including blood pressure, gastrointestinal symptoms, and fasting concentrations of phosphorus, calcium, magnesium, albumin, glucose, insulin, cholesterol, LDL-cholesterol, HDL-cholesterol, triglycerides, urea nitrogen, bicarbonate and C-reactive protein. For all parameters, baseline values will be compared to values at the end of each diet phase (weeks 2 and 4).

9) **Procedures involved**

a. Design.

We will conduct an unblinded, quasi-experimental, controlled feeding study, which will be coordinated through the New York University – Health and Hospitals Corporation Clinical and Translational Science Institute (CTSI). Throughout the study, participants will be prescribed patiromer by the study nephrologist ([name]), which will be administered through the CTSI pharmacy. After a 1-week stabilization period, in which participants are prescribed Patiromer while following their usual diets, the feeding component of the study will occur in two phases. During the first phase (week 2), participants will be transitioned to a plant-rich renal diet, which contains moderate protein (10-15% of kcal), restricts dairy products (≤ 1 serving/day), and eliminates high-potassium fruits and vegetables. During the second phase (weeks 3 and 4), the diet will be altered to provide at-least half of fruits and vegetables from high-potassium sources. To reduce participant burden, meals will be delivered to participants by Portable Chef (New York, NY) three times per week.

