iii. Serum potassium concentrations. The primary purpose of this study is to evaluate the efficacy of patiromer for maintaining serum potassium concentrations in CKD patients during transition to a liberalized plant-rich diet by comparing fasting serum potassium concentrations at screening to values at the end of phase I (week 2) and phase II (week 4) of the study. However, because potassium concentrations are also being used to titrate the dose of patiromer needed to achieve normal potassium concentrations, fasting serum potassium concentrations will also be measured at the end of weeks 1 and 3. To ensure a rapid response to changes in serum potassium concentrations, blood samples obtained at the CTSI CRC will be immediately delivered to the study laboratory at Tisch Hospital for analysis, and the results sent to the CTSI Pharmacy for evaluation (section 10.a.i.). Participants will be directed to pick up new prescriptions from the CTSI Pharmacy on the days of measurement. To obtain a measurement of serum potassium concentration, a 0.5 mL sample of blood is required.

iv. Blood pressure. Systolic and diastolic blood pressures will be measured after 5-minutes of rest in a seated position with their arm supported at the level of their heart and their feet resting on the floor using an automatic sphygmomanometer. Blood pressure measurements will be obtained in duplicate with a third measure obtained if the systolic or diastolic values on repeated measurement differ by more than 5 mmHg.

v. Gastrointestinal symptoms. The frequency and severity of participant gastrointestinal symptoms in the previous week (abdominal cramping, abdominal discomfort, indigestion, infrequent or difficult to pass bowel movements, flatulence, loose or watery stools) will be self-reported via an investigator-developed questionnaire at baseline, and at the end of the stabilization period (week 1), phase I diet (week 2), and phase II diet (week 4).

vi. Other biochemical parameters. Fasting blood samples will be obtained at the CTSI CRC, and analyzed for concentrations of phosphorus, calcium, magnesium, albumin, glucose, insulin, cholesterol, LDL-cholesterol, HDL-cholesterol, triglycerides, urea nitrogen, bicarbonate and C-reactive protein. Similar to serum potassium concentrations, blood samples will be delivered by study staff to the laboratory at Tisch Hospital for analysis. To obtain these biochemical measurements, approximately 5.0 mL of blood is required.

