Table 4. Summary of study visits and procedures

	Screening	Baseline	Wk 1	Wk 2	Wk 3	Wk 4
Baseline Questionnaire (comorbidities, sociodemographics, tobacco and alcohol use, use of dietary supplements and urine output)		X				
Medical Chart Review (cause of CKD, comorbidities, urine albumin concentration)		X				
Medical Chart Review (medications)		X		X		X
Dietary Assessment (3-day food record)			X			
Anthropometrics (height)	X					
Anthropometrics (weight)	X			X		X
Fasting Blood Test (potassium)	X		X	X	X	X
Fasting Blood Test (phosphorus, calcium, magnesium, albumin, glucose, insulin, cholesterol, LDL-cholesterol, HDL-cholesterol, triglycerides, urea nitrogen, bicarbonate and C-reactive protein)		X		X		X
Blood Pressure (systolic and diastolic blood pressure)		X		X		X
Gastrointestinal Symptoms Questionnaire (frequency and severity of abdominal cramping, abdominal discomfort, indigestion, infrequent or difficult to pass bowel movements, flatulence, loose or watery stools in previous week)		X	X	X		X

10) Data and Specimen Banking

No samples will be stored for future analyses in this study.

11) Data Management

Information to be obtained from participants includes height and weight, blood pressure, medical history, blood tests, and self-administered questionnaires (sociodemographics, clinical and comorbid conditions/ management, cigarette and alcohol use and gastrointestinal symptoms). None of the data to be collected is considered sensitive in nature. Some of the participant data such as laboratory results will be linked to the participant's name. Other data (e.g., height, weight, blood pressure, medical history, and surveys) will be linked to the participant through a subject ID number. As a further measure to protect participants' privacy, different subject ID numbers will be used for study measurements and for coordinating the feeding component of the study. We will maintain separate files for identified and de-identified data in locked file cabinets in a locked office. Access to these data will be restricted to the PI ([name]), and study staff responsible for gathering data and maintaining research files. Data will be entered into a centralized database maintained on a secure server. Data

in these files will be linked to participants only through their ID number – this file will be maintained in a locked filing cabinet at [name]. All data collected will be used expressly for the purpose of the proposed study.

a. Overview.

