Once half of the participants are enrolled and accrued, the PI ([name]) will review serum potassium concentrations to ascertain if there were any episodes of moderate-severe hyperkalemia, or protocol issues that require reporting, withdrawing a participant and/or stopping the study. An AE is any unfavorable and unintended sign, symptom, or disease, including worsening of pre-existing medical conditions. The criteria for withdrawing participants are outlined in section 14 below. The study will be stopped if there is a serious adverse event (SAE) related to the study. Any SAE related to the intervention will be reported to the NYU School of Medicine Institutional Review Board by phone and email within 24-hours of being notified. To minimize participant risk and facilitate monitoring, we plan to enroll cohorts of ≤ 2 participants rather than a single cohort of 10 participants. Summary data and safety monitoring reports will be submitted to the NYU School of Medicine Institutional Review Board during annual review, or if there are changes in the risk/benefit ratio of the study.

As per our Clinical Trial Agreement with Relypsa, Inc., the PI will undergo training in reporting AEs by Relypsa, Inc. before starting the study, and will report all AEs that occur after the signing of informed consent, and up to 14 days after the intervention to the Drug Safety and Pharmacovigilance (DSPV) Department at Relypsa, Inc within 15 days of completing the study. Any AEs that are considered serious (SAEs), which occur will be reported to Relypsa, Inc. DSPV Department within 24-hours of being identified/reported. SAE include “any untoward medical occurrence that at any dose: (i) results in death; (ii) is immediately life threatening (i.e. in the opinion of the investigator, the AE places the subject at immediate risk of death; it does not include a reaction that, had it occurred in a more severe form, might have caused death); (iii) requires inpatient

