Another intervention feature to lower the risk of hyperkalemia is the close monitoring of participants’ serum potassium concentrations to adjust the dose of patiomer (10.a.i. Table 2). We will measure serum potassium concentrations as per current patiomer recommendations (weekly), and samples will be processed through the Tisch Laboratory, and the results sent to the CTSI Pharmacy for review. If values are abnormally high or rapidly increasing towards hyperkalemia (10.a.i. Table 2), the study nephrologist ([name]) will be immediately contacted. Because hemolysis can cause artificially elevated serum potassium values, participants with abnormally high or rapidly increasing concentrations of serum potassium will have another blood test to confirm their serum potassium concentrations.

In addition to risks associated with hyperkalemia, there are potential risks related with patiromer use. In a sample of 734 patients treated with patiromer, the most common AEs were constipation (7.2%), hypomagnesemia (5.3%), diarrhea (4.8%), nausea (4.8%), abdominal discomfort (2.0%) and flatulence (2.0%). It is likely that the most common of these AEs (constipation, hypomagnesemia, diarrhea) would be attenuated by a plant-rich diet, which contains higher amounts of fiber and magnesium compared to the typical Western diet. The less common adverse events (abdominal discomfort, flatulence) may be exacerbated by the higher intakes of dietary fiber. These potential AEs will be assessed at the end of each week through the gastrointestinal symptoms questionnaire, and blood testing at the end of phase I and II (for hypomagnesemia). Patiromer also has the potential to bind to other medication, reducing their absorption. This will be mitigated by directing patients to take patiromer once daily, and at least 3 hours away from other medications.

It is unlikely that women and men with stages 3-4 CKD will become pregnant or impregnate someone. Additionally, we will exclude anyone who is planning on becoming pregnant from the study. As part of our Clinical Trial Agreement with Relypsa, Inc., we will report any pregnancies (whether female or male impregnating a female) to Relypsa, Inc. In addition, because the patiromer and the research diets are untested in pregnant women, we will withdraw women who become pregnant during the study period.

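### Section 12 promises weekly assessment of patiromer side effects by GI questionnaire, but the schedule omits week 3 and the listed items omit nausea

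*Combined protocol and SAP*

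**What the plan says.** Section 12 lists the known side effects of patiromer: "the most common AEs were constipation (7.2%), hypomagnesemia (5.3%), diarrhea (4.8%), nausea (4.8" percent, then abdominal discomfort and flatulence at 2.0% each. It goes on: "These potential AEs will be assessed at the end of each week through the gastrointestinal symptoms questionnaire", with blood tests at the end of phases I and II for hypomagnesemia.

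Section 9.b.v sets the questionnaire's timing: "at baseline, and at the end of the stabilization period (week 1), phase I diet (week 2), and phase II diet (week 4". Table 4 marks the same four occasions and leaves the week 3 cell empty. The table lists the content as "abdominal cramping, abdominal discomfort, indigestion, infrequent or difficult to pass bowel movements, flatulence, loose or watery stools in previous week". Section 9.b.v gives the same six symptoms and the same one-week recall, and says that the investigators developed the form themselves.

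Two other provisions bear on week 3. Section 9.a starts the liberalized diet then: "During the second phase (weeks 3 and 4), the diet will be altered" so that at least half of fruits and vegetables are high in potassium. Section 9.b.iii provides a visit: "fasting serum potassium concentrations will also be measured at the end of weeks 1 and 3".

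On reporting, section 12 says that the principal investigator "will report all AEs that occur after the signing of informed consent, and up to 14 days after the intervention", under the agreement with the company that supplies the drug.

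**The concern.** The safety section and the schedule disagree, and staff will work from the schedule. Anyone following Table 4 will hand out no GI form at week 3, and because recall is one week, the week 4 form does not reach back to cover it. A symptom that began and settled in week 3 would be recorded only if the participant volunteered it.

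Week 3 is a poor week to leave out. It is the first week of the diet whose safety the study sets out to test. It may also be the first week on a new patiromer dose, because potassium at the end of week 2 can change the dose and new prescriptions are collected on the day of measurement (sections 9.a.i and 9.b.iii).

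Separately, a participant with nausea has no item on the form under which to report it.

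At stake is the completeness of the adverse event report to the company and the safety summary to the review board. Mild GI symptoms could be undercounted in both.

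**Working it through.** The plan gives no figure to reproduce. The check sets the provisions side by side and then gauges the size.

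**Weeks.** Section 12 implies forms at the end of weeks 1, 2, 3 and 4. Section 9.b.v and Table 4 both give weeks 1, 2 and 4, plus baseline. Text and table agree, so the empty week 3 cell is not damage from PDF extraction. The opening of section 9.b names weeks 1 and 3 as default measurement times, but that default yields to any item with its own schedule, and item v has one.

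**Forms.** With 10 participants (section 5):

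- promised on treatment: 4 × 10 = 40
- scheduled on treatment: 3 × 10 = 30
- missing: 40 − 30 = 10, all in week 3

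**Items.** The five GI events in section 12 against the six items:

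| Event (section 12) | Rate | Matching item |
|---|---|---|
| Constipation | 7.2% | infrequent or difficult bowel movements |
| Diarrhea | 4.8% | loose or watery stools |
| Nausea | 4.8% | none |
| Abdominal discomfort | 2.0% | same name |
| Flatulence | 2.0% | same name |

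Four of five have an item. Indigestion is the nearest to nausea, but section 12 names nausea as an event in its own right.

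**Likely number of events.** Assume that the quoted rates, from 734 treated patients, apply over these four weeks.

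- The four events with an item: 7.2 + 4.8 + 2.0 + 2.0 = 16.0%, so 10 × 0.160 = 1.6 events expected. With onset spread evenly over four weeks, 1.6 / 4 = 0.4 would begin in week 3. The documents do not give the timing; the limits are 0 (none begin in week 3) and 1.6 (all do).
- Nausea: 10 × 0.048 = 0.48 cases expected over the study. The chance of at least one is 1 − 0.952^10 = 38.9%. At half the rate it is 1 − 0.976^10, about 22%; at double, 1 − 0.904^10, about 64%.

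Only week 3 events that settle before the week 4 recall period and go unmentioned at the week 3 visit would be lost, so the loss is smaller than the number that begin.

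**The case against.** The strongest reply is that this is a slip of wording in section 12. The form already follows patiromer alone (week 1), the new diet (week 2) and the liberalized diet (week 4). Participants are seen at week 3 and can mention symptoms, and correcting section 12 to match Table 4 would remove the contradiction. That would make the document consistent. It would also withdraw a safety commitment that an existing visit can meet at almost no cost.

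On nausea, the two sentences just before the weekly commitment discuss constipation, hypomagnesemia, diarrhea, abdominal discomfort and flatulence, and leave nausea out. On that narrow reading every promised GI symptom has an item. This stands as far as it goes: a broken promise on nausea is arguable. The gap remains that an event listed at the same rate as diarrhea is not asked about. The questionnaire itself is not in the documents, so the point rests on the item list, given identically in two places.

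The size is also small. Ten missing forms count forms, not lost events, and the expected loss is well below one event on even spread.

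A reader might infer that week 3 matters because fiber rises then, since section 12 says: "The less common adverse events (abdominal discomfort, flatulence) may be exacerbated by the higher intakes of dietary fiber". The documents do not support that. The comparison there is with a typical Western diet, and the plant-rich diet starts in week 2, which has a form. Table 3 keeps the protein, grain and dairy rules the same in both phases; only the mix of low- and high-potassium fruits and vegetables changes.

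**Conclusion.** The inconsistency over week 3 is certain on the documents. The missing nausea item is a gap in ascertainment whichever way section 12 is read. Severity is minor. Potassium is measured at week 3 as planned, and the GI outcome comparisons use the ends of the diet phases (weeks 2 and 4), so no planned result changes. The effect is a possible undercount of mild events: about 0.4 with onset in week 3 and 0.48 cases of nausea over the study, if the quoted rates carry over and onset is even.

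Two stronger readings are not supported. A reader might infer that the plan fails to collect adverse events in the 14 days after the intervention, since Table 4 ends at week 4. The visible text describes no contact then, but it contradicts nothing, and instructions may sit in the consent pages or the agreement with the company, neither of which is available here. This is a query only. A reader might also infer from section 13 that adverse event follow-up stops at withdrawal. The reporting commitment in section 12 makes no exception for withdrawn participants, and pregnancy leads to withdrawal yet is still reported to the company, so the sentence plausibly concerns outcome data.

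**What to change.** 1. In section 9.b.v and Table 4, add the GI questionnaire at the existing week 3 visit. State that the week 3 form is for safety only and that the outcome comparisons at weeks 2 and 4 stay as planned.
2. Add a nausea item to the form at every administration, including baseline, so that later reports can be read against a starting value. The form is the investigators' own, and nothing in the text suggests that adding an item would disturb a validated instrument.
3. As a query, ask the investigators to confirm how non-emergency adverse events in the 14 days after the intervention will be collected.

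The cost is 10 extra forms (one per participant), one more item per form and a small amendment, with no new visit or laboratory test. The downside is that a few more minor events will be recorded, and without a control group they cannot be attributed to the diet or to patiromer.

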a) Change in medications that alter potassium homeostasis (e.g., RAAS inhibitors, diuretics, β -blockers) in the last month

b) Diagnosed with bowel diseases or syndromes (e.g., bowel obstruction, major GI surgery, short-bowel syndrome, irritable bowel syndrome, inflammatory bowel disease, chronic diarrhea)

c) Dietary restrictions (e.g., allergies) or otherwise unable/unwilling to adhere to study diets (excludes dietary restrictions on high-potassium foods)

d) Pregnant (females) or planning to become pregnant (males and females) during the study

If at any point during the study (including baseline) a participant has moderate-severe hyperkalemia (potassium \geq 6.5mEq/L), or if a participant becomes pregnant during the study, they will be withdrawn from the study.

Inclusion of women and minorities

Given the pilot nature of the intervention and small sample size (n=10), the study population will not be representative of the CKD population, and will have insufficient power to detect differences in intervention effects by sex and race/ethnicity. To our knowledge, plant-rich diets, such as those being investigated in this study, have similar health effects by sex and race/ethnicity. No individual will be excluded from the study on the basis of sex or race/ethnicity alone, and we will attempt to obtain a sample that reflects the demographics of our source population.

5) Study-Wide Number of Subjects

We will recruit a total of 10 individuals to the study. We have secured the support of the New York Harbor VA Healthcare System, which served approximately 250 non-dialysis CKD patients in the New York City area, as well as the Division of Nephrology at NYU Langone Health. It is estimated that approximately 10% of these patients have hyperkalemia. Thus, we have no concerns about our ability to access and recruit the required number of participants for this study. The estimate demographic breakdown of patients at the renal clinic are 95% male with 40% white, 25% black, 20% Hispanic, 10% Asian, and 5% other racial/ethnic background. The planned enrollment is outlined in Table 1.

Table 1. Planned enrollment report

Racial Categories	Ethnic Categories				Total
	Not Hispanic or Latino		Hispanic or Latino		
	Female	Male	Female	Male	
American Indian/ Alaskan Native	0	0	0	0	0
Asian	0	1	0	0	1
Native Hawaiian or Other Pacific Islander	0	0	0	0	0
Black or African American	0	2	0	1	3
White	1	3	0	1	5

More than 1 race	0	1	0	0	1
Total	1	7	0	2	10

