i. Patiromer. Patiromer dosing will be determined based on fasting potassium concentrations measured at the end of each week, factoring in both the absolute concentration, as well as the rate of change. The baseline dose of patiromer will correspond to the study by Weir et al. (2015); 8.4-g once per day for participants with a baseline serum potassium of ≥ 5.1 mEq/L. The following dosing schedule (Table 2) will be used for managing hyperkalemia during the study:

Table 2. Dosing of patiromer during the study based on serum potassium concentrations

Potassium	Change in Potassium	Action
<3.8 mEq/L	Same or decreased	Contact study nephrologist to determine dose
<3.8 mEq/L	Increased	Continue with current dose
3.8-5.0 mEq/L	Changed <0.5 mEq/L	Continue with current dose
3.8-5.0 mEq/L	Changed ≥ 0.5 mEq/L	Continue with current dose, but notify study nephrologist
5.1-6.0 mEq/L	Decreased	Continue with current dose
5.1-6.0 mEq/L	Same or increased	Contact study nephrologist to determine dose
>6.0 mEq/L	Decreased	Continue with current dose, but notify study nephrologist
>6.0 mEq/L	Same or increased	Contact study nephrologist to determine dose

ii. Research Diets. The guidelines for research diets are outlined in Table 3. With the exception of the Dairy Food Group, diets will be balanced according to the USDA MyPlate. Diets will be based on a 7-day menu cycle, and will be reviewed by participants during the screening visit. In order to promote participant adherence with the diets, participants will be permitted to select appropriate substitutes based on their food preferences from a list of pre-approved substitutes. For example, if a participant does not like to eat apples, they may substitute this for a list of other low-potassium fruits.

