Lastly, participants in the study are at risk of breaches of confidentiality. A variety of measures will be used to prevent breaches of confidentiality. First, all study staff will be trained in the NYULMC Practice Fundamentals, which include training in issues of confidentiality. Additionally, all study staff will be required to sign a confidentiality agreement. Although study staff may have access to sensitive information about the participant as recorded in their medical record, only that information pertinent to the study outcomes will be abstracted from the medical record. Data will be maintained as described above (see section 12). We will take steps to avoid participants' perceptions of coercion in the recruitment process.

13) Withdrawal of subjects

As mentioned previously, participants may be withdrawn from the study without their consent in the event that they become pregnant, or they are non-adherent with the research diets. Non-adherence to the research diets will be defined as consumption of >25% of energy from non-research diet foods, which will be assessed at the end of phase I of the study. In the event that involuntary withdrawal is required, participants will be referred back to their treating physician of record for evaluation and management. Data collection will cease at the time of withdrawal.

14) Risks to subjects

Most of the risks associated with this study are outlined in section 13 along with corresponding measures to protect against these risks (include hyperkalemia, patiromer side effects and interactions with medications, and breach of confidentiality). Blood tests will be drawn for this study, which are sometimes accompanied by bruising, bleeding, and minor tenderness at the puncture site. Participants will be made aware of all of these risks prior to enrolling in this study.

15) Potential Benefits of the Proposed Research to the Subjects and Others

Participants may experience some temporary improvement in cardiometabolic risk factors and serum potassium concentrations related to intervention; however, this is not guaranteed. Moreover, any temporary improvements in these conditions are unlikely to have any lasting benefits to participants.

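### The mandatory withdrawal at potassium of 6.5 mEq/L or higher is missing from the withdrawal section and from Table 2, and section 11 does not say how participants withdrawn for it are analysed

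*Combined protocol and SAP*

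**What the plan says.** - **Section 4, after the exclusion criteria.** The trigger is potassium of 6.5 mEq/L or higher: "If at any point during the study (including baseline) a participant has moderate-severe hyperkalemia". The consequence is mandatory: "or if a participant becomes pregnant during the study, they will be withdrawn from the study".
- **Section 12.** The reader is sent elsewhere for the withdrawal rules: "The criteria for withdrawing participants are outlined in section 14 below". Section 14 is the section on risks; withdrawal is section 13.
- **Section 13.** Involuntary withdrawal is worded as permitted, not required, "in the event that they become pregnant, or they are non-adherent with the research diets". Potassium is not among the reasons. The same section says that data collection ends when a participant is withdrawn.
- **Section 9.a.i, Table 2.** There are two rows for potassium above 6.0 mEq/L, neither with an upper limit. If potassium has decreased, the action is "Continue with current dose, but notify study nephrologist". If it is the same or higher, the action is "Contact study nephrologist to determine dose". Neither row mentions 6.5 or withdrawal.
- **Section 12, on monitoring.** Because hemolysis can falsely raise potassium, participants with abnormally high or rapidly rising values "will have another blood test to confirm their serum potassium concentrations".
- **Sections 9.b.iii and 11.** The primary comparison is fasting potassium at screening against the end of weeks 2 and 4. The analysis is repeated-measures ANOVA with Tukey's test, plus the proportion with hyperkalemia at each time point. Missing data are mentioned only as a feature that may call for special methods.

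**The concern.** Section 12 names cardiotoxicity from hyperkalemia as the major risk of the study. The one mandatory rule for it stands among the eligibility criteria. It is absent from the section cited for withdrawal criteria and from the table that governs the response to the weekly results sent to the pharmacy. Someone working from either place would not find it.

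The rule also shapes the primary data. Withdrawal is triggered by the primary outcome itself and ends data collection. The participants who lose their later values are therefore those in whom potassium was not maintained. Without an analysis rule for them, later summaries lean towards the hypothesis that patiromer maintains normal potassium.

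**Working it through.** The plan has no figure of its own to reproduce on this point. The check sets the passages side by side and then follows the data.

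**1. Which instruction meets a value of 6.5 or higher?**

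| Place | Instruction |
|---|---|
| Section 4 | Withdraw, mandatory |
| Section 12 | See the withdrawal section (wrong number) |
| Section 13 | Potassium not listed |
| Table 2, above 6.0, decreased | Continue the dose and notify |
| Table 2, above 6.0, same or increased | Nephrologist determines the dose |

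**2. Which Table 2 row applies?** Accrual requires a screening value from 5.1 to below 6.5 (section 6). A first value of 6.5 or higher is therefore a rise from every earlier value and falls in the same-or-increased row. The decreased row can apply at 6.5 or higher only if an earlier value was also that high. By then section 4 would already have acted, unless a repeat draw is read against the first draw. The documents do not address that case.

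**3. What is lost, by visit of the trigger?** Table 4 schedules potassium at screening and weeks 1, 2, 3 and 4.

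| Trigger at | Week 2 value | Week 4 value |
|---|---|---|
| Week 1 | lost | lost |
| Week 2 | measured (the trigger) | lost |
| Week 3 | measured earlier | lost |
| Week 4 | measured earlier | measured (the trigger) |

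If the repeated-measures ANOVA over screening, week 2 and week 4 were run on complete cases, any participant triggering at weeks 1 to 3 would drop out entirely. That includes a triggering value measured at week 2. Section 11 does not say whether complete cases will be used.

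**4. Effect on the week 4 proportion (illustration).** Suppose one of 10 is withdrawn before week 4 and x of the other nine are hyperkalemic at week 4.

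- Observed values only: x/9.
- Withdrawn participant counted as not maintained: (x + 1)/10.
- Difference: (x + 1)/10 − x/9 = (9 − x)/90.
- x = 0: 0/9 = 0% (95% Clopper-Pearson interval 0 to 34%) against 1/10 = 10% (0.3 to 45%).
- x = 2: 2/9 = 22.2% against 3/10 = 30.0%, a difference of 7/90 = 7.8 points.
- Two withdrawn and none of the other eight hyperkalemic: 0/8 = 0% (0 to 37%) against 2/10 = 20% (2.5 to 56%).

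**5. How likely is it to arise?** The documents give no event rate. Let p be each participant's assumed chance of reaching 6.5 before week 4. The chance of at least one such participant among 10 is 1 − (1 − p)^10.

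| p | At least one of 10 |
|---|---|
| 2% | 18% |
| 5% | 40% |
| 10% | 65% |
| 20% | 89% |

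**The case against.** The strongest reply is that there is no competing rule. Section 4 is explicit and applies at any point in the study. Section 13 does not call its list complete, and section 12 itself links episodes of moderate-severe hyperkalemia to withdrawing a participant. The permissive wording in section 13 carries little weight, because section 12 makes withdrawal mandatory for the same two reasons. Table 2 can be read as dosing for participants still enrolled, and its top rows have their own use between 6.0 and 6.5. All of this stands. The list is incomplete where the reader is told to look; it is not a contrary instruction.

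Two stronger readings are tempting, and the documents support neither.

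- A reader might infer that Table 2 keeps participants at 6.5 or higher on their current dose. A first such value falls in the row where the nephrologist determines the dose (step 2), and no passage says that these participants remain in the study.
- A reader might infer that the highest values disappear from the week 2 and week 4 means. Section 13 stops collection; it does not delete what was collected. A trigger at week 2 or week 4 is already a measured value at that visit, and a trigger at week 4 loses nothing. A shift in the mean obtained by deleting a measured 6.5 therefore does not follow, and a later missing value is unknown, not 6.5.

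It can also be said that a test done to confirm a value implies action on the confirmed result. That is a natural reading, but section 4 does not state it.

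**Conclusion.** The point holds as a gap in cross-referencing and in the analysis plan. The withdrawal rule for the study's main risk is missing from the section cited for it and from Table 2, and the value that triggers it is not defined. Followed as written, section 4 together with the end of data collection removes later potassium values from participants who failed on the primary outcome.

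The bias runs one way, in favour of the hypothesis. With 10 participants, one withdrawal before week 4 lowers the reported week 4 proportion by up to 10 percentage points compared with counting that participant as not maintained. This rests on at least one participant reaching 6.5 before week 4, for which the documents give no rate, and on the withdrawn participant being counted as a failure. The effect on the ANOVA arises if it is run on complete cases, which section 11 leaves open. No size is claimed for any shift in mean potassium.

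**What to change.** **Protocol wording.** The sponsor must reconcile sections 4, 12 and 13 and Table 2 into one rule for values of 6.5 mEq/L or higher. The rule should be cross-referenced from each place, with the section number corrected, and should state whether the first or the confirmed value triggers it. What the rule should be is a clinical matter, and none is proposed here.

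**Section 11.** Add that:

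- the triggering value is kept at the visit where it was measured;
- a participant withdrawn for potassium of 6.5 or higher counts as hyperkalemic (not maintained) at each later scheduled summary visit with no measured value, while values measured earlier stand;
- the hyperkalemia proportion is reported over all participants who started treatment;
- these participants are listed with the triggering value and visit;
- they are not dropped from the analysis of change, for example by using a mixed model on all available values. The week 1 and week 3 values should be included, so that the value that led to withdrawal is in the model.

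The second item must not overwrite measured values. A normal week 2 result before a week 3 trigger remains normal.

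**Cost.** A short wording amendment and a few sentences in the analysis section. No new data or visits are needed.
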